Data analysis	
The primary endpoint, the change from Baseline to 3 years in the CogState Global Cognitive Composite Score (GCCS), will be analyzed using a repeated measures analysis of covariance (ANCOVA) model in which treatment, age stratification factor, MMSE stratification factor, region, education level, apolipoprotein E <math>\epsilon</math>4 allele (APOE4) status (carrier vs. non-carrier), baseline cerebrovascular disease burden as measured by MRI (calculated based on four factors: lacunar infarcts > 2; cortical or subcortical infarct > 1cm^3; white matter lesion Fazekas score of 3; micro hemorrhages <math>\geq</math>4), visit (Weeks 26, 52, 78, 104, 130, and week 156) and treatment-by-visit interaction are included as fixed-effect factors and baseline GCCS and visit by baseline GCCS interaction as covariates, with a common unstructured covariance matrix among visits between treatment group. The adjusted mean changes at 3 years within each treatment group and standardized treatment group difference (Cohen's d) in mean change from baseline at 3 years will be presented with corresponding 95% confidence interval (CI) based on the above model. The primary analysis will be based on Safety set (SAF) including 'on-treatment' data collected prior to the start of treatments for AD or cognitive impairment.
 
The secondary efficacy variables are:
 
 
1. Change from baseline in individual cognitive domains (memory, executive function, and attention) as assessed by the individual components of the cognitive assessment battery at 3 years.
 
2. Change from baseline in the summary score of the instrumental activities of daily living (IADL) as assessed with Functional Activity Questionnaire (FAQ) at 3 years.
 
 
These secondary efficacy variables will be analyzed in a similar manner as the primary endpoint (GCCS).
 
Safety endpoints to be analyzed are:
 
 
1. Change from baseline in a cortical composite SUVr (standardized
 

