#### Study Population:

The study population will consist of patients 60 years and older with chronic heart failure (NYHA class II-IV) and LVEF > 40%. LCZ696 has been shown to improve survival and reduce heart failure-related hospitalization in patients with HFrEF (LVEF ≤ 40%). Hence the study population consists of patients with HFpEF (LVEF >40%), as it is considered unethical to randomize HFrEF patients in this long term study to the valsartan treatment group. HFpEF is a condition that predominantly affects an elderly population. Age is also an important risk factor for cognitive decline and amyloid deposition. The entry requirement of 60 years or older and symptomatic heart failure will ensure that patients who are likely to benefit from LCZ696 therapy are included in the study while allowing the ability to study the potential effects on cognitive function in a relevant population. As treatment with LCZ696 has been demonstrated to confer significant mortality and morbidity benefit compared to current standard of care (ACEI) to patients with HFrEF, these patients will be excluded from the study. However, given the similarity of the population and patient characteristics, the results of this study should be relevant to the heart failure population at large regardless of ejection fraction.

The study aims to assess the effect of LCZ696 compared to valsartan on cognitive function in patients with normal cognition and mild cognitive impairment (MCI), while excluding patients with significant impairment, (e.g. patients with an MMSE score of <24; [Holsinger et al 2007](#)). Available data suggest that amyloid plaque deposition may reach a plateau once a patient is clinically diagnosed with AD ([Bateman et al 2012](#)). The rate of cognitive decline in AD patients is not uniform as it is dependent on various factors. Hence patients with a clinical diagnosis of AD or dementia will also be excluded from this study.

Further details about the patient population are provided in [Section 4](#).

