Captopril	100 mg	Candesartan	16 mg
Cilazapril	2.5 mg	Eprosartan	400 mg
Enalapril	10 mg	Irbesartan	150 mg
Fosinopril	20 mg	Losartan	50 mg
Imidapril	10 mg	Olmesartan	10 mg
Lisinopril	10 mg	Telmisartan	40 mg
Moxepril	7.5 mg	Valsartan	160 mg
Perindopril	4 mg		
Quinapril	20 mg		
Ramipril	5 mg		
Trandolapril	2 mg		
Zofenopril	30 mg		

Randomized treatment epoch

At the end of treatment run-in, patients who meet the protocol specified safety criteria as assessed by central or local laboratories and tolerate LCZ696 100 mg bid for at least 2 weeks are eligible for randomization. Patients will be randomized in a 1:1 fashion to either LCZ696 200 mg bid or valsartan 160 mg bid. The randomization will be stratified based on age (< 75, ≥ 75 years), MMSE score (< 28, ≥ 28), and baseline brain amyloid status (unknown, amyloid positive, amyloid negative).

With an expected screening and run-in failure rate of approximately 40%, it is estimated that approximately 870 patients will be screened at more than 150 centers worldwide to randomize approximately 520 patients. A subset of about 430 randomized patients will be enrolled in the amyloid PET imaging substudy.

There is no formal interim analysis planned for efficacy. Interim safety data will be reviewed by an external Data Monitoring Committee (DMC) regularly as specified in the DMC charter. The final analysis is planned to be executed at the completion of all planned assessments for last randomized patient.

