2.2.1 Subgroup of interest

Subgroups will be formed to explore the consistency of treatment effects and safety profiling on selected parameters between the subgroups and the overall population.

In general, subgroups will be defined based on baseline information. In this study, since we have a run-in phase to test patients' tolerability to the study drugs before they can enter the double blind phase, we have defined two baselines ([Section 2.1](#)): the run-in baseline and the double-blind baseline. Subgroups will be formed using one of these baselines according to their analysis purposes.

In [Table 2-1](#), we have listed all subgroups defined for this study and the ways to derive them. Subset of these subgroups will be used depending on the parameter under consideration. Also note that only important parameters or variables in these analyses will have subgroup analyses. The details about the parameters having subgroup analyses will be presented in the corresponding sections as appropriate. Also, additional subgroups may be formed later for regional or country-wide analyses.

Table 2-1 Specification of subgroups

Subgroup	Method of derivation	Background & Demographics / Exposure	Efficacy	Safety
Age groups: (<65 vs. ≥65 years)	Screening (derived)		X (CogState GCCS)	
Age groups: (<75 vs. ≥75 years)	Screening (derived)	X	X	X
Gender (male/female)	Screening	X	X	X
Region*	Derived (pooled countries or country), using Screening data	X	X	X
Education level (<12, ≥12 years)	Derived using screening data		X	X
Baseline MMSE cut-off (<28, ≥28)	Derived using MMSE at randomization	X	X	X
Baseline LVEF cut-off (<50%, ≥50%)	Screening		X	X
Baseline NYHA class (I/II and III/IV)	Derived using randomization data for DB phase and screening data for run-in phase		X	X
APOE4 allele status** (+/+, -/+, -/-)	Randomization		X	X (Dementia related AE summaries)
Baseline brain amyloid status (unknown, positive, negative)	Randomization	X	X	X
Baseline cerebrovascular disease burden***	Screening	X	X	X (Dementia related AE summaries)
Baseline diabetes mellitus (Yes, No)	Screening		X (CogState GCCS)	
SBP status (≤140, >140 mmHg)	Randomization		X (CogState GCCS)	

* **North America:** USA, Canada

Latin America: Argentina

Western Europe: Belgium, France, Germany, Italy, Spain, Switzerland, UK, Netherland

Central Europe: Bulgaria, Croatia, Lithuania, Russia, Turkey, Poland

Asia Pacific and Others: Australia, Korea, Taiwan

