2.3.2 Demographic and baseline characteristics

For the run-in phase, summary statistics will be provided by total number of patients based on the enrolled set (ENR) for background and demographic characteristics, disease characteristics, and cardiovascular risk factors for the run-in phase baseline (Screening visit), including the following parameters:

- **Continuous variables:** Age (in years), weight (in Kg), height (in cm), body mass index (BMI, in kg/m²), education level (number of years), number of years of continuous employment, number of HF hospitalizations in last 12 months, Ejection fraction (in %), NT-pro-BNP, systolic blood pressure (in mmHg), diastolic blood pressure (in mmHg), pulse (in bpm), MMSE overall summary score

- **Categorical variables:** Age group (<65 years vs. ≥65 years; <75 years vs. ≥75 years), sex, race, ethnicity, country, region, education level (<12, ≥12years), category of prior CV medication, prior HF hospitalization (yes/no), NYHA class, NT-pro-BNP, and MMSE category (<28, ≥28).

BMI will be calculated as weight (kg) / height² (m²) from the collected height and weight at Visit 1 (Screening Visit).

Similarly, for the double-blind phase, summary statistics will be provided by randomized treatment group and overall based on the Safety set for the above mentioned parameters in addition to: APOE4 allele status, baseline SUVr value, amyloid status (positive/negative)

at baseline.

Demographic and baseline characteristics will be similarly summarized for patients in the SAF who participated in the PET imaging sub-study.

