2.5.2 Statistical hypothesis, model, and method of analysis

The change from baseline in the GCCS of CogState test battery will be analyzed using a repeated measures analysis of covariance (ANCOVA) model in which treatment, age stratification factor, MMSE stratification factor, education level, APOE4 status (carrier vs. non-carrier), baseline cerebrovascular disease burden, visit (Weeks 26, 52, 78, 104, 130 and Week 156) and treatment-by-visit interaction are included as fixed-effect factors and baseline GCCS and visit-by-baseline GCCS interaction as covariates, with a common unstructured covariance matrix among visits between treatment groups. The adjusted mean changes at 3 years (Week 156) within each treatment, the difference in mean changes at 3 years (Week 156) between the two treatments, and its 95% confidence interval obtained from the above model will be presented. In addition, the treatment difference (LCZ696-valsartan) in mean changes from baseline to 3 years will also be expressed based on a standardized effect size (Cohen's d) with a 2-sided 95% confidence interval. The Cohen's d will be estimated by using the adjusted between-treatment mean difference, divided by the estimated pooled standard deviation. The estimated standard deviation for the mean difference is:

$$SD = \left(\frac{1}{n_1} + \frac{1}{n_2} \right)^{1/2} \hat{\sigma}$$

where n1 and n2 are the number of patients within each treatment group and $\hat{\sigma}$ is the pooled standard deviation of the within treatment group adjusted mean change. Cohen's d can be rewritten in terms of t value of the estimated between treatment group difference based on the adjusted mean changes from the model mentioned above:

$$t = \frac{\hat{\mu}_1 - \hat{\mu}_2}{SD} = \frac{\hat{\mu}_1 - \hat{\mu}_2}{\left(\frac{1}{n_1} + \frac{1}{n_2} \right)^{1/2} \hat{\sigma}}$$

$$\hat{d} = \frac{\hat{\mu}_1 - \hat{\mu}_2}{\hat{\sigma}} = \left(\frac{1}{n_1} + \frac{1}{n_2} \right)^{1/2} \times t$$

Confidence interval (CI) of Cohen's d is based on 95% CI of the noncentrality parameter of t value divided by the square root of the degrees of freedom from the estimated between treatment group adjusted mean change (Cumming and Finch 2001). The analysis is based on a direct likelihood method with an assumption of missing at random (MAR) for the missing data mechanism.

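### The primary model uses age and MMSE only as two-level strata and leaves out region, which the protocol synopsis lists: a small loss of precision, with one inconsistency to reconcile

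*SAP*

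**What the plan says.** SAP 2.5.2 lists the fixed effects of the primary model as "treatment, age stratification factor, MMSE stratification factor, education level, APOE4 status (carrier vs. non-carrier") and cerebrovascular burden at baseline, followed by visit and treatment-by-visit. Baseline GCCS and its interaction with visit are continuous covariates. Protocol 9.4.2 gives the same list.

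The strata come from the randomization, which SAP 1.1 describes as stratified by "age (< 75, ≥ 75 years), MMSE score (< 28, ≥ 28), and baseline brain amyloid status (unknown, amyloid positive, amyloid negative"). Age and MMSE therefore each contribute one two-level factor.

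The data analysis entry of the protocol summary describes the same primary model with "treatment, age stratification factor, MMSE stratification factor, region, education level", so region appears there and nowhere else for this endpoint. Region is available: SAP Table 2-1 defines five regional groups, "Derived (pooled countries or country), using Screening data". It is also a term in the SUVr imputation model and ANCOVA (protocol 9.5.2, SAP 2.7.1). SAP 2.3.2 summarizes "Age (in years), weight (in Kg), height (in cm") and the "MMSE overall summary score" as continuous variables. SAP section 4 records no change to the protocol-specified analyses.

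**The concern.** The protocol itself says "Age is also an important risk factor for cognitive decline and amyloid deposition" (section 3.2). Entry starts at 60 years, so the model gives a patient of 60 and one of 74 the same age adjustment. The same holds for MMSE scores of 24 and 27. Where the outcome varies with age or MMSE within a stratum, that variation stays in the residual, and the standard error of the treatment difference is larger than it needs to be.

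Region raises a second, simpler issue. Someone who reads only the synopsis would expect a different primary model from the one that will be run, and no text explains the difference.

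**Working it through.** **Reproducing the plan's figure.** Inputs from SAP 3.1: d = 0.3, two-sided 5%, 180 per group.
- Required n per group = 2 × (1.960 + 0.842)² / 0.3² ≈ 175 (176 with the t distribution). The plan states 180.
- Power at 180 per group: 81.2% by the normal approximation, 81.0% by the noncentral t.
- 360 / 0.70 ≈ 515 to randomize. The plan states 520.

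The stated design reproduces. It assumes no covariate gain, so the sample size is not in error.

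**How much of age the split keeps.** The documents give no age distribution for this trial, so one has to be assumed. The share kept is the squared correlation between age and the <75/≥75 indicator.
- Age N(72, 7) truncated at 60: 0.641.
- Mean 70.9, SD 9.4 (the earlier HFpEF study in protocol 1.1), truncated at 60: 0.667; without truncation: 0.594.

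**Gain from continuous age.** Let r be the assumed partial correlation of age with 3-year change, given the other terms. With f = 0.641, the further share of residual variance removed is g = r²(1 − f) / (1 − f r²). The SE of the raw difference is multiplied by √(1 − g). Power to exclude 0 is taken at the raw difference that equals d = 0.3 under the current model (noncentral t, 180 per group).

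| r | g | SE multiplier | Power |
|---|---|---|---|
| 0 (current model) | 0 | 1 | 81.0% |
| 0.15 | 0.00808 / 0.98558 = 0.8% | 0.996 | 81.3% |
| 0.20 | 0.01436 / 0.97436 = 1.5% | 0.993 | 81.6% |
| 0.30 | 0.03231 / 0.94231 = 3.4% | 0.983 | 82.3% |

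On the scale of 520 randomized patients, 520 × g is about 4 to 18. With f = 0.667 the variance range is 0.8% to 3.2%, so the choice of age distribution matters little.

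**Adding MMSE and region.** This is illustrative only. Three assumed MMSE distributions over 24–30 give a share kept of 71% to 75% for the split at 28. With added R² of Ra, Rm and Rr for age, MMSE and region, taken as additive, the variance ratio is (1 − Ra − Rm − Rr) / (1 − 0.67 Ra − 0.71 Rm). Power here uses the normal approximation, so it starts from 81.2%.
- (0.01, 0.01, 0.01): 0.970 / 0.9862 = 0.984; SE × 0.992; power 81.9%.
- (0.05, 0.03, 0.03): 0.890 / 0.9452 = 0.942; SE × 0.970; power 83.5%.
- (0.10, 0.05, 0.05), the top of the assumed range: 0.800 / 0.8975 = 0.891; SE × 0.944; power 85.4%.

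**Effect on Cohen's d.** SAP 2.5.2 sets d = t × √(1/n₁ + 1/n₂), with the model's own SD in the denominator. The residual SD cancels from the interval width. On the d scale the half-width is about 1.96 × √(2/180) = 0.207 whatever the covariates. However the noncentrality limits are rescaled, only n and the degrees of freedom enter. What does move is d itself: a raw difference worth 0.300 now becomes 0.300 / √(1 − g), which is 0.301 to 0.305 with continuous age. In the illustrative cases with all three terms it becomes 0.303 to 0.318.

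**The case against.** The case for leaving the model alone is reasonable. Adjusting for the stratification factors as randomized is conventional and valid, and all three descriptions of the model use age and MMSE in that form. Continuous baseline GCCS, with its visit interaction, is already included and probably carries much of the MMSE information. The size of the gain rests on correlations that the documents do not supply, and at the low end it is under 1% of variance. All of this stands, and it is why the point is minor.

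Three stronger readings are tempting, and the documents support none of them.
- A reader might infer that the coarse strata widen the interval that must exclude 0.3. That interval is for d, and its width does not depend on residual variance under the SAP formula. The probability of excluding 0.3 when there is no difference would hardly change.
- A reader might infer that the SAP departs from the protocol while declaring no change. Its covariate list matches protocol 9.4.2, the full statistical section. Only the synopsis differs, so the conflict lies within the protocol and concerns region alone.
- A reader might infer that the primary model is still open to choice. SAP version 5.0, dated before database lock, gives one covariate list and one ordered fallback for non-convergence.

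One objection also bears on the remedy. Because d uses the model SD, adding covariates changes what 0.3 means on the raw scale, so the covariates should not be changed without settling that SD.

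**Conclusion.** The point holds as a minor matter of precision and consistency. Baseline information already collected is not fully used, and region is stated for the primary model in one place and missing in two. Nothing here biases the treatment comparison or invalidates the sample size.

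From age alone, the gain is 0.8% to 3.4% of residual variance. The SE of the raw Week 156 difference falls by about 0.4% to 1.7%, and power to exclude 0 at d = 0.3 rises from about 81.0% to 81.3–82.3%. This rests on the assumed partial correlations of 0.15 to 0.30 and the assumed age distribution. MMSE and region could add to it, but the documents give nothing from which to size their part. The benefit falls on the raw difference and on the second design goal, excluding 0. It does not fall on the goal of excluding 0.3 when the treatments are equal.

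**What to change.** Before unblinding:
1. In SAP 2.5.2, add continuous age and continuous baseline MMSE score alongside the two strata, and keep the strata. Use the same model for the cognitive domains and FAQ (SAP 2.6.2).
2. Reconcile region across the protocol synopsis, protocol 9.4.2 and SAP 2.5.2. The preferable route is to add it, as the synopsis and the SUVr model do. Otherwise, remove it from the synopsis with a reason. Record the decision in SAP section 4.
3. State which SD defines Cohen's d, and fix it so that the 0.3 margin does not shift with the covariate set. If that SD is no longer the model's own, the shortcut from t to d no longer applies, and the interval method must be restated to match.

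The cost is about six extra parameters (one for age, one for MMSE, four for five regions) and no new data. The main downside is the third item: d must be tied to a fixed SD, otherwise the added covariates change the scale on which the primary conclusion is read.

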#### 9.4.2 Statistical model, hypothesis, and method of analysis

The change from baseline in the GCCS of CogState test battery will be analyzed using a repeated measures analysis of covariance (ANCOVA) model in which treatment, age stratification factor, MMSE stratification factor, education level, APOE4 status (carrier vs. non-carrier), baseline cerebrovascular disease burden as measured by MRI (calculated based on four factors: lacunar infarcts > 2; cortical or subcortical infarct > 1cm^3; white matter lesion

Fazekas score of 3; micro hemorrhages  $\geq 4$ ), visit (Weeks 26, 52, 78, 104, 130 and Week 156) and treatment-by-visit interaction are included as fixed-effect factors and baseline GCCS and visit by baseline GCCS interaction as covariates, with a common unstructured covariance matrix among visits between treatment group. The adjusted mean changes at 3 years (Week 156) within each treatment, the difference in mean changes at 3 years (Week 156) between the two treatments, and its 95% confidence interval obtained from the above model will be presented. In addition, the treatment difference (LCZ696-valsartan) in mean changes from baseline to 3 years will also be expressed based on a standardized effect size (Cohen's d) with a 2-sided 95% confidence interval. The Cohen's d will be estimated by using the adjusted between-treatment mean difference, divided by the estimated standard deviation, which is calculated from the standard error of the adjusted mean change and the sample number of patients within each group (the pooled SD) from the above modeling. The analysis is based on likelihood method with an assumption of missing at random (MAR) for missing data.

As the primary analysis, this repeated measure ANCOVA model will be performed in the Safety set including 'on-treatment' data collected prior to the start of treatments for AD or cognitive impairment. The Cohen's d based on the adjusted difference in mean changes at 3 years (Week 156) between two treatments and its 95% confidence interval from this model will be used to draw the main conclusion for the primary objective. On-treatment data refer to cognitive test data collected while patients are on-study-medication (regardless of treatment interruption) or within three months after final study drug intake date.

In addition, the same repeated measure ANCOVA model will be performed in the following two analysis sets as supportive analyses:

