2.5.3 Handling of missing values/censoring/discontinuations

The repeated measure ANCOVA modeling as described in the previous section is based on a direct likelihood method with an assumption of missing at random for the missing data mechanism. That means, missing data, including those from dropouts, will be implicitly predicted based on similar patients. By similar we mean patients with similar baseline covariates, measurement histories and who were randomized to the same treatment arm. Various analyses to assess the sensitivity of the primary analysis results to the MAR assumption are described in [section 2.5.5](#).

Data collected more than three months after patients permanent discontinuation of the study medication will be excluded from analyses in both the Safety and PPS analyses. In addition, data collected after patients starting treatments for AD or cognitive impairment will be excluded from “on-treatment” analyses.

Patients with no post-baseline assessments available will be excluded from the primary analysis. However, these patients will contribute to the imputation model for the missing GCCS scores in the sensitivity analyses.

Table 2-3 Overview of missing data handling in analyses for primary endpoint

Analysis	Analysis Set	Data excluded	Missingness assumption	Analysis method	Time points included	Imputed dataset required?
Estimand: The treatment effect had all patients stayed ‘on-treatment’ for the 3-year planned follow-up duration (Under ‘as-treated’ principle)						
Primary	SAF	Off-treatment (>3 months after last dose) After start of treatment for AD or cognitive impairment	MAR	Repeated measure ANCOVA	Weeks 26, 52, 78, 104, 130 and Week 156	No
Sensitivity to Primary analysis	SAF	Off-treatment (>3 months after last dose) After start of treatment for AD or cognitive impairment	MNAR for missing data due to death, HF hosp., stroke	Tipping point analysis followed by ANCOVA	Baseline, Weeks 26, 52, 78, 104, 130 and Week 156	Yes

	SAF	Off-treatment (>3 months after last dose) After start of treatment for AD or cognitive impairment	MNAR for missing data after starting treatments for AD or cognitive impairment	Tipping point analysis followed by ANCOVA	Baseline, Weeks 26, 52, 78, 104, 130 and Week 156	Yes

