3.1 Sample size calculation for the primary endpoint

It is currently estimated that approximately 180 patients per group having data on 3-year planned follow up –

- Would provide at least 80% probability that the 2-sided 95% confidence interval (CI) excludes a standardized effect size (Cohen's d) of 0.3 (or greater) in change in composite z-score of the battery test over 3 years, given that there is no expected difference between two treatments.
- Would provide at least 80% probability that the 2-sided CI excludes 0 (corresponding to $p < 0.05$), if the true effect size is 0.3 or greater (in either direction).

An effect size of 0.3 in Cohen's d corresponds to a margin of $0.3 \times SD$ ($SD =$ standard deviation) on the original scale for the difference between treatments in mean global score change from baseline, and is generally considered as small (Cohen 1988). In a systematic review of studies for health-related quality of life instruments that have reported the minimally important difference (MID), it was found that for the majority of studies the MID estimates were consistently close to $0.5 \times SD$ (Norman et al 2003). In addition, socially accepted benchmarks for conditions that induce cognitive impairment such as low level alcohol intoxication within legal driving limit in most countries (0.05%) are generally associated with declines of 0.3 or higher for psychomotor speed, attention and working memory. Therefore, the sample size of the study was determined to be able to detect (or exclude) effect sizes in the magnitude of 0.3 in Cohen's d with high probability, as it appears to be an appropriate choice to guide the interpretation of the cognitive function results.

In addition, defining the magnitude of the MID using a measure of effect size, rather than a raw difference score has additional advantages:

- Expressing the magnitude of an important difference in scale free units (Cohen's d) allows models of clinically meaningful difference to be based on integration of outcomes from a broad set of studies whose characteristics are relevant to the current study (i.e. magnitude of change in cognition related to amyloid, magnitude of change occurring after heart failure, and magnitude of change related to cardiovascular disease).

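### The SD behind Cohen's d is back-calculated from the repeated-measures standard error and an undefined patient count, so d depends on retention as well as on effect

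*SAP*

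**What the plan says.** Protocol 9.4.2 divides the adjusted between-treatment difference by an SD that is "calculated from the standard error of the adjusted mean change and the sample number of patients within each group". SAP 2.5.2 puts this into formulas. The standard error of the difference is set equal to sqrt(1/n1 + 1/n2) times σ̂, where σ̂ "is the pooled standard deviation of the within treatment group adjusted mean change". Then "Cohen's d can be rewritten in terms of t value of the estimated between treatment group difference", which gives d = sqrt(1/n1 + 1/n2) × t. The sizes are described only by the clause "where n1 and n2 are the number of patients within each treatment group". Nothing says whether this means the Safety set, the patients who enter the model, or those observed at Week 156.

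Three other statements bear on this:

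- The model is a six-visit likelihood analysis "with a common unstructured covariance matrix among visits between treatment groups" (SAP 2.5.2). It therefore already estimates a Week 156 residual SD.
- SAP 2.5.3 states that "Patients with no post-baseline assessments available will be excluded from the primary analysis".
- The planned sample size allows for a 30% loss of information over 3 years (Protocol 9.8.3, SAP 3.3).

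Both documents rest the main conclusion for the primary objective on d and its 95% confidence interval. The design aims to detect or exclude d = 0.3. SAP 2.6.2 carries the same d over to the domain scores and the FAQ.

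**The concern.** The identity SE = SD × sqrt(1/n1 + 1/n2) belongs to a two-sample comparison with complete data. In a repeated-measures model with dropout, the Week 156 standard error depends on three things: the outcome SD, how many Week 156 values are missing, and how much the earlier visits recover. Solving for an SD with a simple head count folds all three into σ̂. Two trials with the same true effect and the same outcome SD, but different retention, would then report different values of d.

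The comparison with 0.3 is what suffers. If σ̂ is too large, d shrinks and 0.3 is easier to rule out. That is the less safe direction for a trial prompted partly by a theoretical amyloid risk (Protocol 1.1). If σ̂ is too small, the reverse holds. The count is undefined, so the choice between these outcomes would still be open when the data are analysed.

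**Working it through.** **1. The plan's own figure.** SAP 3.1 gives about 180 per group with 3-year data for "at least 80% probability that the 2-sided 95% confidence interval (CI) excludes a standardized effect size" of 0.3. On the d scale (SD = 1), n = 2 × (1.960 + 0.842)² / 0.3² = 174.4, so 175. At 180 the power is 81%. Allowing for 30% loss, 360 / 0.70 = 514.3, so 515, against about 520 planned. The figure reproduces.

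**2. What the formula returns.** Let σ be the Week 156 residual SD and define the effective sample size per arm by SE = σ × sqrt(2/n_eff). Then:

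- σ̂/σ = SE / (σ × sqrt(2/n)) = sqrt(n/n_eff)
- reported d = true d × sqrt(n_eff/n)

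The formula is right only if n = n_eff, which is not a count of patients.

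**3. Inputs.** From the documents: 520 randomised 1:1 (260 per arm), 30% loss, six visits. Assumed, because the documents give none: monotone dropout with 95, 90, 85, 80, 75 and 70% observed at successive visits, and compound-symmetry (CS) or AR(1) correlations. This gives per arm:

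- 260 in the Safety set, taking all randomised patients as dosed;
- 260 × 0.95 = 247 with at least one post-baseline visit;
- 260 × 0.70 = 182 observed at Week 156.

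**4. Effective n and reported d for a true d of 0.30.** SE² is twice the Week 156 diagonal element of the inverse of the per-arm information, which is summed over the dropout patterns (13 patients last seen at each of the first five visits, 182 complete). With σ = 1, n_eff = 2/SE². For example, CS 0.7 gives SE = 0.0962 and n_eff = 216.1. With n = 260, σ̂/σ = sqrt(260/216.1) = 1.097, and d = 0.30/1.097 = 0.274.

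| Correlation | n_eff | d, n = 260 | d, n = 247 | d, n = 182 |
|---|---|---|---|---|
| CS 0.5 | 201.3 | 0.264 | 0.271 | 0.316 |
| CS 0.7 | 216.1 | 0.274 | 0.281 | 0.327 |
| CS 0.8 | 225.1 | 0.279 | 0.286 | 0.334 |
| AR(1) 0.7 | 192.9 | 0.258 | 0.265 | 0.309 |
| AR(1) 0.8 | 200.5 | 0.263 | 0.270 | 0.315 |
| AR(1) 0.85 | 206.5 | 0.267 | 0.274 | 0.320 |

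n_eff runs from 193 to 225 and matches none of the three counts. A 2,000-run simulation at correlation 0.7 gave 0.275, 0.282 and 0.329 for the three counts, and 0.302 with the model's own Week 156 SD.

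**5. Consequence for excluding 0.3, if the interval were scaled like d.** Take half-width 1.96 × h with h = sqrt(2/n), and f = sqrt(n_eff/n). The chance of excluding a true 0.3 is Φ(0.3 × (1 − f)/h − 1.96). For CS 0.7 and n = 247, h = 0.0900 and f = 0.935, so Φ(0.216 − 1.96) = Φ(−1.745) = 4.1%. Over the table, against a nominal 2.5%:

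- n = 260: 4.3% to 6.9%
- n = 247: 3.5% to 5.8%
- n = 182: 1.1% to 2.1%

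By symmetry these hold for either sign of d.

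**6. Test against 0.** d is t times a positive constant, so this conclusion does not change.

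**7. Residual SD against raw change SD.** With equal variances and baseline to Week 156 correlation r, the change score has variance 2σ₀²(1 − r) and the baseline-adjusted residual has σ₀²(1 − r²). The SD ratio, residual to raw, is sqrt((1 + r)/2): 0.975 at r = 0.9 and 0.866 at r = 0.5. A d on the residual SD is therefore larger by a factor of 1.03 to 1.15.

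**The case against.** **Direction.** A reader might infer that d is always biased toward zero. The documents do not support that. It follows if n counts the Safety set or the modelled patients, and it reverses if n counts patients with Week 156 data. SAP 3.1 does describe its planning n as patients with 3-year data. Nor is 260 the best-supported of the larger counts, because SAP 2.5.3 keeps patients without a post-baseline assessment out of the primary analysis. About 247 fits that text better. This objection stands.

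**Error rates.** A reader might also infer that the plan as written carries a 3.5-7% chance of wrongly excluding 0.3. It cannot be read that way. SAP 2.5.2 forms the interval by dividing the noncentrality limits by the square root of the degrees of freedom, so n1 and n2 do not enter that step. This is a separate error, and a larger one if applied literally. With 180 per group and d = 0.30, limits consistent with d are 0.092 to 0.508, while the written rule gives 0.046 to 0.254, which excludes its own point estimate. The rates in step 5 apply only once the interval is on the same scale as d.

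**Which SD is right.** The model's residual SD is conditional on baseline GCCS and covariates, whereas SAP 3.1 explains 0.3 in terms of the SD of change from baseline. With n = 247, the formula gives 0.88 to 0.95 of the residual-scale d. Multiplied by 1.03 to 1.15, that is about 0.91 to 1.10 of the raw-change d, so the formula may land close to that scale by accident. This rules out calling the repair free of trade-offs. It does not rescue a quantity that moves with retention.

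**Stakes.** The plan looks for effects in both directions, shrinkage is conservative for claiming benefit, and the unstandardised difference with its interval is also reported. All of this is true and limits the harm. The main conclusion is still drawn from d.

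**Conclusion.** The defect is in the text: the SD that scales d is not the Week 156 SD, and the count needed to compute it is undefined. Under the stated assumptions, the same data with a true d of 0.30 would be reported anywhere from about 0.26 to 0.33, depending on which count the programmer uses. That is anti-conservative for excluding 0.3 if n counts all or all modelled patients, and conservative if n counts those seen at Week 156. The size is moderate and rests on assumed visit correlations and an assumed monotone dropout pattern; different retention would move it. The mechanism and the dependence of the direction on n do not rest on those particular values. The plan should be changed, together with the confidence interval rule in the same section.

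**What to change.** Before unblinding, amend SAP 2.5.2 as follows:

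- Define d as the adjusted Week 156 difference divided by the square root of the Week 156 diagonal element of the fitted common covariance matrix. If the compound-symmetry fallback is used, divide by the square root of its total variance.
- Put the confidence interval on the same scale as d, replacing the division by the square root of the degrees of freedom.
- State that this SD is conditional on baseline and covariates, so d will be somewhat larger than on the raw change-score SD (about 3-15% for assumed baseline to Week 156 correlations of 0.9 to 0.5). Report d on the raw change SD as a check.
- Apply the same rule to the domain scores and the FAQ (SAP 2.6.2), and to the d reported in the tipping-point analyses (SAP 2.5.5).

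The cost is SAP wording and a small code change, since the fitted model already provides the SD. The trade-off is that the sponsor must say openly which SD the 0.3 margin refers to. No new data are needed.
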